1.3 Secondary Study Endpoints

The secondary endpoints include subjective ratings of the films and side effects.

2.0 Background

2.1 Scientific Background and Gaps

According to the CDC, cigarette smoking is associated with profound morbidity and mortality. In the United States alone, cigarette smoking is responsible for about 480,000 deaths per year¹ and costs the nation more than \$300 billion annually.² About 15% of all adults smoke in the United States and by 12th grade, 42% of students report having smoked. Starting, however, is one problem and stopping is another. Cigarette smoking is a disease of chronic relapse. Indeed, once having started, smokers will make as many as 20 quit attempts before they are successful³ and abstinence rates can be as low as 7%, even following NRT with the patch, gum, or nasal spray.⁴ As with other addictions, cue-induced craving contributes to relapse following a quit attempt.⁵

From a global perspective, it would seem that there are three options for the treatment of cigarette smoking: no support (unaided cessation), behavioral support of one manner or another, and/or pharmacological intervention. With nearly 70% of smokers reporting that they would like to quit, yet most failing, we must assume that will, alone, is not sufficient. Certainly, the ability to quit any addiction can be bolstered by behavioral and/or pharmacological support. Contingency management is a behavioral intervention where abstinence is reinforced with tangible incentives such as money. However, individuals addicted to smoking may be insensitive to the very reward upon which their behavior is contingent.^{6,7} NRT is a long-standing and widely used smoking cessation tool. Yet, as discussed, NRT too is only modestly effective. We propose that the limited effectiveness of NRT is due, at least in part, to a failure to prevent cue-induced craving and relapse. In support, NRT treatment does not attenuate stimulus-elicited drug seeking. Here we propose a novel alternative to the steady-state delivery of nicotine (i.e., to the standard patch) for the treatment of smoking cessation. Specifically, we propose to use an oral film to treat smokers wishing to quit with random, rather than steady-state, delivery of nicotine prior to and following the quit date.

2.2 Previous Data

Support for our random delivery hypothesis is provided by both preclinical and clinical data suggesting that yoked (i.e., uncontrollable/unpredictable) delivery of drug impairs the development of cue-drug associations, retards or disrupts responding for drug or alcohol, and can even render the drug aversive. In rats, yoked delivery of ethanol retarded later acquisition of ethanol self-administration⁸ and, in our hands, a history of yoked delivery of cocaine⁹ disrupted the willingness to work for the drug on a progressive ratio schedule of reinforcement. Although fixed ratio (FR) responding appears normal in rats with a history of yoked delivery of cocaine, the averaged data occlude the fact that rats yoked to high

drug-takers actually took only about 4 infusions/hour on the FR schedule. To be effective, however, yoked delivery of drug needs not only delay acquisition in drug inexperienced rats, but must effectively rescue subjects with a strong drug habit. In accordance, Twining and Mueller (in preparation) found that yoked delivery of cocaine rescued cocaine-experienced rats by reducing drug seeking during extinction and by reducing drug-taking during subsequent FR testing. In humans, Donny et al¹⁰ reported that yoked delivery of cocaine led to an increase in mean systolic and diastolic blood pressure in response to the drug because of a lack of cue-supported tolerance. Scheduled availability of ethanol led to a marked decrease in intake of ethanol in a controlled setting.¹¹ Finally, a meta-analysis showed that pre-cessation treatment with a standard (i.e., steady state) nicotine patch doubled the odds of quitting smoking relative to subjects that received only post-cessation treatment with the nicotine patch.¹²⁻¹⁴ Rose and Behm, too, found abstinence enhanced by pre-cessation treatment with the nicotine patch.¹⁵ [name] reported that use of the nicotine patch while smoking led to a 14% reduction in expired carbon monoxide (CO), reduced satisfaction from smoking, and fewer and weaker reported urges to smoke.¹⁶ These marked effects are thought to be due, at least in part, to separation of blood nicotine levels from the act of smoking.¹⁵ Dissociation of smoking behavior and cues from nicotine is expected to be even greater with random nicotine delivery.

2.3 Study Rationale

There is, as yet, no 'random patch'. Random delivery via a subcutaneously placed chip or pump is conceivable, but would be invasive and expensive. Here we propose to test the merits of our hypothesis simply by using a trans-mucosal nicotine orally dissolving film that has been tested and is safe for use in humans.^{17,18} In a pharmacokinetics study, we found that plasma nicotine levels achieved by the nicotine film are similar to those resulting from consumption of equivalent doses of other oral NRT products.¹⁹ The films were well-tolerated in this study and produced mild side effects that were similar in nature to those of currently available NRT.¹⁹ The film is easy to use and tastes pleasant to humans. No water is required, as the film simply adheres to the roof of the mouth until dissolved (less than 5 minutes). Indeed, unlike nicotine gum, there are no complicated instructions regarding how and when to chew. The film can be used to deliver any dose of nicotine desired over time and placebo films are readily available. Finally, if the hypothesis proves correct, this novel treatment should be fairly inexpensive and available over the counter. As such, it will be both accessible and affordable, even for low-income smokers.

If this 'random film' were to work as predicted, cigarette cues would be dissociated from the act of smoking, smokers maintained on the random film would be more likely to achieve cessation. This would be a remarkable advance for the treatment of smoking and would inform the treatment of other addictions as well.

3.0 Inclusion and Exclusion Criteria

3.1 Inclusion Criteria

1. Aged 18-55
2. Smoke ≥ 10 cigarettes/day for at least the past 12 months
3. Exhaled CO measurement ≥ 6 ppm at baseline visit
4. Interested in completely ceasing cigarette consumption and using a nicotine film product as directed
5. Willing to attend regular visits over a 6-week period (not planning to move, not planning extended vacation, no planned surgeries)
6. Able to read and write in English
7. Able to understand and consent to study procedures

3.2 Exclusion Criteria

1. Unstable or significant medical conditions and conditions such as elevated blood pressure (systolic >159 mmHg or diastolic >99mmHg at baseline), COPD, and those conditions that are likely to affect participant safety such as kidney or liver disease
2. Individuals with sodium-restricted diet, heart disease, recent heart attack, irregular heartbeat, stomach ulcers, or diabetes as well as those taking prescription medications for depression or asthma as indicated under “Warnings” section on FDA approved NRT Drug Facts Label
3. More than weekly use in the past 3 months of illegal drugs or prescription drugs that are not being used for medically prescribed purposes
4. Use of non-cigarette nicotine delivery product in the prior 7 days (including cigars, pipes, chew, snus, hookah, electronic cigarette and marijuana mixed with tobacco)
5. Use of an FDA approved cessation medication in the past 7 days (any NRT, Chantix, Wellbutrin)
6. Women who are pregnant (verified by urine pregnancy test at baseline visit), trying to become pregnant, or nursing
7. Uncontrolled mental illness or substance abuse or inpatient treatment for these conditions in the past 6 months
8. Any previous adverse reaction to NRT
9. Any other condition, serious illness, or situation that would, in the investigator’s opinion, make it unlikely that the participant could comply with the study protocol
10. Other member of household currently participating in the study

3.3 Early Withdrawal of Subjects

3.3.1 Criteria for removal from study

The PI reserves the right to remove a participant from the study for any reason, based on their discretion in order to protect the safety of a participant.

3.3.1.1 Withdrawal prior to randomization

Participants who meet any criteria below at Visit 2 will be considered for withdrawal prior to randomization:

- Not smoking ≥10 cigarettes/day for at least 5 out of the past 7 days
- Use of a non-cigarette nicotine delivery product in the past 7 days
- Reporting a quit attempt in the past 30 days

3.3.1.2 General withdrawal criteria

Participants may be discontinued by the PI at any point during the study for any of the following reasons:

- **Missing their study visit window:** If a participant misses their study visit window, the participant will be considered for withdrawal from the study.
- **New pregnancy:** Participants who report a new pregnancy at any point during the study will be withdrawn.
- **Cardiovascular disease (CVD) event requiring inpatient hospitalization:** CVD typically includes MI (heart attack), PTCA (angioplasty/stenting), bypass surgery, stroke, peripheral vascular disease (arterial blockages in arms or legs leading to procedure or surgery). Less common CVD problems would be new cardiac arrhythmias (e.g., new atrial fibrillation) or new valvular disease (e.g., mitral or aortic regurgitation).
- **DVT/PE (deep vein thrombosis/pulmonary embolism, i.e., blood clots in the venous system) requiring inpatient hospitalization.**
- **Adverse events related to nicotine film use:** Adverse events, including symptoms of nicotine overdose (nausea, vomiting, dizziness, weakness, or

rapid heartbeat) or allergic reactions to the nicotine film, will be monitored at every study visit.

- **Worsening substance abuse** in which the participant is behaving inappropriately at visits or demonstrates an inability to continue with the study.
- **Any inpatient hospitalization or debilitation** in which participation in the study could be detrimental to the recovery process. This will be self-reported by the participant and will be reviewed by the site PI and medical professional to determine whether continued participation in the study is appropriate (this could include recovery from a major surgery, worsening of psychiatric symptoms, etc.).
- **Any situation where participant is not able to use their study product for a period of more than 2 weeks** (e.g., incarceration or other similar situation) unless they report non-study product use by choice.
- **Participant choice:** Participants may choose to remove themselves from the study by informing the research team in writing at any point during the study. If they choose to remove themselves from the study, they will not receive any further contact from the study center.
- **Participant behavior:** If a participant is behaving in an inappropriate or threatening manner, admits to lying about eligibility criteria, is participating in other smoking research studies that could affect the primary outcome measures, appears/admits to giving away/selling study products, consistently loses study products, etc., then the PI can withdraw him/her from the study at the PI's discretion.

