3.3.2 Follow-up for withdrawn subjects

If participants are withdrawn from the study for any of the reasons noted above prior to randomization, they will be replaced until a total of 45 participants have been randomized to the study. Reasons for withdrawal will be ascertained from subjects who voluntarily withdraw from the study (See End of Trial Form).

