8.3 Statistical methods

Paired sample t-tests (or nonparametric Wilcoxon Rank-Sum tests) will be used to examine changes in the outcome measures (CPD, CO, subjective measures, BP, HR) from baseline.

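### A randomized participant can be withdrawn for missing a visit window, with no outcome follow-up described afterwards and no analysis set or missing-data rule to deal with the gap

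*Combined protocol and SAP*

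**What the plan says.** The general criteria in Section 3.3.1.2 are not limited to the period before randomization: "Participants may be discontinued by the PI at any point during the study for any of the following reasons". One item concerns attendance alone: "If a participant misses their study visit window, the participant will be considered for withdrawal from the study". Visits 3, 4 and 5 have windows of ±3 days (Sections 7.2.4, 7.2.6 and 7.2.8).

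Section 3.3.2 is headed as follow-up for withdrawn subjects but covers two other things. It provides for replacing people withdrawn before randomization, until 45 are randomized, and for recording a reason: "Reasons for withdrawal will be ascertained from subjects who voluntarily withdraw from the study". For people who leave by their own written choice, Section 3.3.1.2 is explicit: "they will not receive any further contact from the study center". For people withdrawn by the PI, neither section mentions further CPD or CO data.

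Section 8.3 says that paired t-tests, or a nonparametric alternative, "will be used to examine changes in the outcome measures (CPD, CO, subjective measures, BP, HR) from baseline". Section 10.7 repeats this. Neither section names an analysis set, a time point or a rule for missing values.

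**The concern.** Missing a visit is an attendance event, not a safety event, and in a quit-smoking trial it may well go with smoking again. A rule that allows such a person to be removed can discard data that could still have been obtained. A paired test needs both values, so without another rule it leaves out anyone without the later one.

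Two things are at stake. One is the size of the reduction reported in each arm. The other is the comparison of random with steady-state and placebo delivery, which is the objective in Section 1.1. Randomization protects that comparison only while the people analysed are those randomized. With 15 per arm, two or three losses are enough to matter.

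**Working it through.** **Inputs from the documents.** There are three regimens (Section 7.4.2), 15 per arm (Section 8.2) and 45 randomized (Section 8.1). 3 × 15 = 45, so the total holds no allowance for loss after randomization, and Section 3.3.2 replaces only losses before it. No attrition rate, effect size, SD, alpha or power is stated.

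**Which data are exposed.** CPD is collected at three phone calls as well as at visits, but CO only at visits. Visit 3 (Day 14) precedes the quit, which starts the next morning (Section 7.2.4.7), so the only post-quit CO values come from Visits 4 and 5. A participant withdrawn after missing Visit 4 has none. That participant may still have post-quit CPD from Phone Call #2, but Section 8.3 does not say whether it would be used.

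**Formula.** Let d be the proportion lost, Rc the mean reduction in completers and Rw that in those lost. All three are assumed below.

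- All-randomized mean = (1 − d) × Rc + d × Rw
- Overstatement by completers = d × (Rc − Rw)

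**Within one arm.**
- d = 3/15, Rc = 70%, Rw = 0: 12/15 × 70 = 56%, an overstatement of 14 points.
- Rc = 80%, Rw = 0, d from 10% to 40%: 0.10 × 80 = 8 to 0.40 × 80 = 32 points.
- Rc = 80%, Rw = 30%, same range of d: 0.10 × 50 = 5 to 0.40 × 50 = 20 points.
- Rw = Rc: no overstatement at any d.

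**Between arms, a difference hidden.** Completers in both arms cut by 70%, those lost return to baseline, and losses are 2/15 (random) and 5/15 (placebo). Completers show 70 − 70 = 0. All-randomized means are 70 × 13/15 = 60.7% and 70 × 10/15 = 46.7%, a difference of 14 points.

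**Between arms, a difference created.** Both arms have a true all-randomized reduction of 50%, those lost have none, and losses are 10% and 30%. Completers show 50/0.9 = 55.6% and 50/0.7 = 71.4%, a spurious 15.9 points in favour of the arm with more loss.

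**Counting missing as baseline smoking.** Take 2/15 and 5/15 again, but suppose that those lost also cut by 70%. The true difference is 0, yet the imputed means are 60.7% and 46.7%. The rule then creates 14 points, so it is not conservative between arms when loss differs.

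**Precision.** Assuming two-sided alpha 0.05 and 80% power, going from 15 to 12 analysable per arm (20% loss) raises the detectable two-arm difference from 1.06 to 1.20 SD and the detectable paired change from 0.78 to 0.89 SD.

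**The case against.** The strongest reply is that the rule is discretionary. A participant is only considered for withdrawal, and the PI may decide otherwise. Retention is also supported by reminders (Section 7.2.9) and by payments tied to Visit 5 (Section 14). This stands as a limit on how often the rule will bite. It does not supply criteria for the decision, or outcome data once the decision is made.

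A second reply is that a completer analysis is nowhere stated. That is correct. It is the default of a paired test when no other rule is given, and the absence of follow-up after PI withdrawal is inferred from silence. Section 8.3 also contains no between-arm test, so the between-arm bias concerns the comparison the objective calls for, not one the plan specifies.

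Four stronger readings are tempting, and the documents do not support them:

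- A reader might infer that not using films leads to withdrawal. The item reads "Any situation where participant is not able to use their study product for a period of more than 2 weeks" and adds "unless they report non-study product use by choice". On the natural reading, choosing not to use films is exempt, though the phrase is ambiguous and should be clarified. Section 11 also allows product use to stop for oral effects without tying that to leaving the study.
- A reader might infer that every listed criterion leads to withdrawal. Most are discretionary, and the adverse-event item says only that events will be monitored.
- A reader might infer that reductions are overstated in every arm. That requires those lost to have reduced less than those retained, which is plausible but not documented.
- A reader might infer that Section 11 expects unequal loss. It says that placebo participants may have more serious withdrawal symptoms. It predicts no dropout, and it also lists nicotine side effects, which could cause loss in the active arms.

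**Conclusion.** The point holds in a limited form. The plan permits an attendance-based withdrawal after randomization, describes no CPD or CO collection after a PI-initiated withdrawal, and has no analysis set or missing-data rule. Followed as written, it can lose obtainable outcome data in groups of 15.

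The direction of bias rests on one assumption, that those lost reduced less than those retained. The size cannot be fixed from the documents. In the illustrations above, the within-arm overstatement runs from 0 to 32 points, and unequal loss moves the between-arm difference by about 14 to 16 points. These figures come wholly from assumed inputs and are not forecasts for this trial. The change is worth making because it is cheap, not because a large bias has been shown.

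**What to change.** - **Section 3.3.1.2.** After randomization, remove the missed window as a ground for leaving outcome follow-up. Accept late CPD and CO data and flag them as out of window. Clarify the exemption in the item on being unable to use films.
- **Section 3.3.2.** For PI-initiated withdrawal, separate stopping films from leaving follow-up. Leave the clinical rules and the film supply unchanged, and keep the remaining scheduled calls and visits for CPD and CO where the participant agrees. Leave the no-contact rule for voluntary withdrawal as it is.
- **Section 8.3.** Analyse all 45 as randomized, using all post-baseline CPD and CO data. Report an analysis counting missing as baseline smoking beside the observed-data analysis. State that this imputation is not conservative between arms if loss differs by arm, and report loss by arm.

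The cost is protocol wording, some out-of-window data and a little more analysis. The calls and visits are already scheduled. Film supply is 14 plus 3 days and sized to the visit window (Section 7.4.6.3), so late data at Visits 3 and 4 may include days beyond the supply, which the flag should make visible. At Visit 5 no films are dispensed, so a late visit there has no supply consequence.

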13.0 Sharing Results with Subjects

This study is not designed to diagnose any disease or condition. However, if during the course of conducting clinical procedures (e.g., blood pressure), a participant is found to have a result outside of clinical norms, the result will be discussed with the participant at the visit where the result is identified. The participant will be given a letter indicating what procedure was done and will direct them to contact a medical provider for further evaluation. If a woman tests positive for pregnancy, the results will be shared with the participant, they will be withdrawn from the study, and they will be advised to follow up with their doctor for prenatal medical care.

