19.0 Adverse Event Reporting

19.1 Adverse Event Definitions

For drug studies, incorporate the following definitions into the below responses, as written:	
Adverse event	Any untoward medical occurrence associated with the use of the drug in humans, whether or not considered drug related
Adverse reaction	Any adverse event caused by a drug
Suspected adverse reaction	Any adverse event for which there is a reasonable possibility that the drug caused the adverse event. Suspected adverse reaction implies a lesser degree of certainty about causality than “adverse reaction”. 
• Reasonable possibility. For the purpose of IND safety reporting, “reasonable possibility” means there is evidence to suggest a causal relationship between the drug and the adverse event.

Serious adverse event or Serious suspected adverse reaction	Serious adverse event or Serious suspected adverse reaction: An adverse event or suspected adverse reaction that in the view of either the investigator or sponsor, it results in any of the following outcomes: Death, a life-threatening adverse event, inpatient hospitalization or prolongation of existing hospitalization, a persistent or significant incapacity or substantial disruption of the ability to conduct normal life functions, or a congenital anomaly/birth defect. Important medical events that may not result in death, be life-threatening, or require hospitalization may be considered serious when, based upon appropriate medical judgment, they may jeopardize the patient or subject and may require medical or surgical intervention to prevent one of the outcomes listed in this definition.
Life-threatening adverse event or life-threatening suspected adverse reaction	An adverse event or suspected adverse reaction is considered “life-threatening” if, in the view of either the Investigator (i.e., the study site principal investigator) or Sponsor, its occurrence places the patient or research subject at immediate risk of death. It does not include an adverse event or suspected adverse reaction that had it occurred in a more severe form, might have caused death.

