19.2 Recording of Adverse Events

Research subjects will be routinely questioned about adverse events at in-person study visits and during scheduled phone contacts.

All adverse events (serious or non-serious) and abnormal test findings observed or reported to study team believed to be associated with the study drug(s) or device(s) will be followed until the event (or its sequelae) or the abnormal test finding resolves or stabilizes at a level acceptable to the investigator.

An abnormal test finding will be classified as an adverse event if one or more of the following criteria are met:

- The test finding is accompanied by clinical symptoms
- The test finding necessitates additional diagnostic evaluation(s) or medical/surgical intervention; including significant additional concomitant drug treatment or other therapy
 - NOTE: Simply repeating a test finding, in the absence of any of the other listed criteria, does not constitute an adverse event.
- The test finding leads to a change in study drug dosing or discontinuation of subject participation in the clinical research study.
- The test finding is considered an adverse event by the investigator.

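### The ban on contact after written withdrawal conflicts with the duty to follow film-associated adverse events, so the course of an event still open at departure may be lost

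*Combined protocol and SAP*

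**What the plan says.** Four parts of the combined protocol and SAP bear on this point.

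- **Section 3.3.1.2, Participant choice.** The route out is a written notice, open throughout the study: "Participants may choose to remove themselves from the study by informing the research team in writing at any point during the study". The next sentence sets the consequence: "If they choose to remove themselves from the study, they will not receive any further contact from the study center". It has no exception for safety.
- **Section 19.2.** Adverse events, serious or not, and abnormal test findings that the team has observed or been told of and believes to be linked to the study product "will be followed until the event (or its sequelae) or the abnormal test finding resolves or stabilizes at a level acceptable to the investigator". It has no exception for people who have left.
- **Section 3.3.2.** Its heading promises follow-up for withdrawn subjects, but its content is limited to replacing people withdrawn before randomization and to this: "Reasons for withdrawal will be ascertained from subjects who voluntarily withdraw from the study". It points to an End of Trial Form, which is not among the documents. It contains no safety follow-up.
- **Sections 10.3 and 10.4.** Adverse events are collected at each visit and call, and participants may report them at any time while the study lasts. Nothing is said about the period after withdrawal.

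**The concern.** The two rules give opposite instructions for the same person. Someone who writes in to leave while a film-associated event is unresolved must be followed under Section 19.2 and must not be contacted under Section 3.3.1.2. Staff who obey the withdrawal rule as written cut off follow-up that the safety section requires.

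What is at stake is the later course of the event: whether it cleared, persisted or became more serious. That matters because the film is investigational and studied under an IND (Sections 7.4.1 and 17.1), because side effects are a secondary endpoint (Section 1.3), and because the medical monitor's judgment of seriousness under Section 19.3 depends on what the team knows. An event that was mild when the notice arrived could worsen, and staff would be barred from finding out.

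The reason for leaving raises a smaller version of the same problem. Section 3.3.2 wants it from everyone who withdraws voluntarily, but a written notice need not give one, and staff could not then ask.

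**Working it through.** No figure in the plan bears on this, so there is nothing to reproduce or recompute. The check is to set the sections side by side and sort the possible departures.

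**Inputs**

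| Rule | Applies to | Instruction |
|---|---|---|
| 3.3.1.2, Participant choice | Written voluntary withdrawal | No contact from the center afterwards |
| 3.3.1.2, other grounds | Withdrawal by the investigator (film-related adverse event, cardiovascular hospitalization, clot, other hospitalization, new pregnancy, and so on) | No ban on contact stated |
| 19.2 | Events known to the team and believed film-associated | Follow to resolution or stabilization |
| 3.3.2 | Voluntary withdrawal | Obtain the reason |
| 19.3 | Documented events | Weekly review of causality and seriousness |

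**Cases**

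1. *Withdrawn by the investigator.* The ban is attached only to Participant choice. Section 19.2 still applies in full, so there is no conflict.
2. *Voluntary withdrawal, no film-associated event open.* Section 19.2 asks for nothing further, so there is no conflict with it.
3. *Voluntary withdrawal after an event the team never heard of.* Section 19.2 covers observed or reported events, so its duty was not triggered. Staff may not ask, but the two rules do not contradict each other.
4. *Voluntary withdrawal with a known film-associated event still open.* Section 19.2 requires follow-up and Section 3.3.1.2 forbids contact. Both cannot be obeyed, unless the participant happens to volunteer the outcome.
5. *Voluntary withdrawal with no reason in the notice.* Section 3.3.2 requires the reason and Section 3.3.1.2 bars asking for it later. If the reason is in the notice, or is taken when the notice is handed over, both can be met.

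**Does another section repair case 4?** Section 3.3.2 does not, because it is silent on safety. Sections 10.3 and 10.4 tie collection to study contacts, and a participant in case 4 has none left. Section 19.3 ensures that what was already documented is reviewed, but it does not supply the later course. No final safety contact for withdrawn participants is described.

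**Result.** Case 4 is a true contradiction and case 5 a conditional one. Cases 1 to 3 are not contradictions.

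**The case against.** The strongest reply is that very little is lost. A reported event is already on record, counts in the safety data, and goes to the medical monitor's weekly review for causality and seriousness. Contacts after Visit 2 are nominally a week apart, so few events should be unknown when someone leaves. The ban runs only from the center to the participant. A participant can still volunteer information, and Section 19.4.1 covers volunteered events. The reason for leaving may be captured on the End of Trial Form at the time of withdrawal. Section 11.0 also lets a participant stop the film for oral effects without describing that as leaving the study. Finally, the consent pages were removed before review, so the consent form may already deal with safety contact after withdrawal.

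Most of this stands, and it narrows the point. An event reported before departure is neither uncharacterized nor beyond a causality judgment. The reason for leaving is often obtainable. The consent form cannot be called deficient. None of it settles case 4: documentation up to the day of leaving is not follow-up to resolution, and relying on the participant to call does not discharge a duty placed on the team.

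Three stronger readings are tempting, and the documents do not support them.

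- *That the ban is why pregnancy outcomes go unobserved.* A reader could connect it with Section 19.1, which counts "or a congenital anomaly/birth defect" among serious outcomes, and Section 13.0, which says only that after a positive test "they will be advised to follow up with their doctor for prenatal medical care". But new pregnancy is a separate ground for withdrawal without the no-contact sentence. Outcome follow-up is not described there, but this rule does not forbid it.
- *That events which make people leave are lost in general.* Withdrawals by the investigator for adverse events or hospitalization remain under Section 19.2.
- *That the film will look better tolerated than it is.* Section 11.0 calls excess-nicotine symptoms unlikely to be severe at these doses and says that placebo participants may have more serious nicotine withdrawal symptoms. The documents give no basis for saying which arm would lose more information.

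**Conclusion.** The point holds in a narrow form. Sections 3.3.1.2 and 19.2 cannot both be followed for a participant who withdraws in writing with a known, unresolved film-associated event, and no other section resolves the conflict. Section 3.3.2 adds a lesser tension over the reason for leaving, which arises only when the notice gives none and nothing was recorded at the time.

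The size cannot be given. The documents state no expected rate of voluntary withdrawal and no rate of film-associated events, so the number affected among the 45 to be randomized is unknown and may be zero. What may be lost is later worsening or resolution, not the record that the event occurred, so an event already reported still counts in its arm's rate.

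The conclusion assumes that the no-contact sentence means what it says and that no removed or separate document, such as the consent form or the End of Trial Form, qualifies it. It is still worth correcting, because a rule followed as written would stop required safety follow-up of an investigational product, and the correction is cheap.

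**What to change.** Reconcile Sections 3.3.1.2, 3.3.2 and 19.2:

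- In Section 3.3.1.2, limit the ban on contact to study visits, study procedures and recruitment.
- State that, unless the participant expressly refuses, staff may make a phone contact to record the reason for leaving and any ongoing event, and will continue the follow-up of film-associated events that Section 19.2 already requires.
- Add cross-references in Sections 3.3.2 and 19.2, and have an express refusal recorded as the explanation when follow-up stops early.
- Check the consent form and make it consistent with the revised text.

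The cost is about a paragraph of protocol text, a consent sentence if one is not already there, and a few calls by existing staff. The downside is slightly more contact with people who have left, which they can decline.
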